COVERING LETTER

From:

[name]

Principal Investigator.

Jawaharlal Institute of Postgraduate Medical Education & Research.

23.02.2021

To,

Clinicaltrial.gov.

Subject : Submission of Study protocol, Statistical analysis plan (SAP) and informed consent form (ICF) .

Dear Sir// Madam,

I, [name], am hereby submitting study protocol, statistical analysis plan (SAP) and informed consent form (ICF) for the following clinical study (details):

Study Title : Comparison of Sulfasalazine versus Leflunomide based combination disease modifying anti-rheumatic drug therapy (DMARD) in patients with Rheumatoid arthritis failing Methotrexate monotherapy : A randomized control trial

NCT number : NCT02930343

Document date : 02.05.2016

Kindly find appropriate documents hereby .

Thanking you.

Best regards.

STUDY PROTOCOL

Background

Rheumatoid arthritis (RA) is a systemic autoimmune disease characterized by inflammatory polyarthritis. The hallmark of RA is symmetric synovial proliferation and inflammation of joints that leads to erosions and progressive destruction of joints leading to disability. Disease modifying anti rheumatic drugs (DMARDs) form the mainstay for RA treatment. Early aggressive treatment of RA can halt or slow down the disease progression and disease, thus decreasing disease related disability and improving the quality of life significantly.

The current strategy for treatment of RA is “treat – to- target” approach (1) to achieve early and sustained remission. Methotrexate is the initial drug of choice for early DMARD naïve patients. Patients not achieving the target for disease control, can be started either on combination of conventional DMARDs therapy or biologic agents (TNF inhibitors) (1)(2). According to the latest EULAR recommendations, addition of a biological DMARD, especially a Tumor Necrosis Factor (TNF) inhibitor, should be considered when poor prognostic factors are present; in the absence of poor prognostic factors, a combination therapy should be considered. (2).

The main hurdle for the use of TNF inhibitors or other biologicals for management of RA in Indian as well as western setting is high cost of therapy. The annual cost for biologic treatment for RA ranges from Rs. 3 lacs (for Rituximab) to Rs. 44 lacs (for Adalimumab), whereas that for combination therapy with Methotrexate (MTX) + Sulfasalazine (SSZ) + Hydroxychloroquine (HCQ) is Rs.15,000 and that of MTX+ Leflunomide (LEF)+HCQ is Rs. 30,000. Also the rate of infections with Biologics is higher especially Tuberculosis in Indian setting. The combination non-biological DMARDs are not only cheaper but also safer alternatives to the biological agents.

However, there are no guidelines to direct the treating physician regarding the choice of combination conventional DMARDs as there are no head to head trials comparing the efficacy, safety and cost effectiveness of various combination DMARDs.

Rationale

Inspite of various advances in field of early diagnosis of RA, there is still a need for better understanding of the efficacy and safety of various combinations of conventional DMARDs, and to rank them in order accordingly, so as to give a clearer vision for further management of RA once MTX monotherapy fails, and to achieve remission as soon as possible.

Novelty

This study will attempt to compare 2 different DMARD combinations (MTX+SSZ+HCQ versus MTX+LEF+HCQ) in terms of its efficacy and safety in the treatment of RA.. Both these regimes are approved and used for the treatment of RA but head to head comparison data is not available.

Expected outcome and application

The results of the study may help to rationalize treatment of patients with RA especially in countries like India where resources are limited and cost is a constraint. The result of the study may also provide evidence for better and prompt management of the disease with appropriate combination therapy once MTX monotherapy fails.

Research Question: which combination of conventional DMARD is better and should be recommended, in terms of efficacy and safety for the treatment of early RA, in patients who fail to respond to Methotrexate monotherapy?

Research Hypothesis: LEF based combination DMARD regimes is inferior to SSZ based combination DMARD therapy in safety and efficacy in patients with RA who fail initial MTX monotherapy.

Aims and Objectives: (PICO format)

Aim : To compare 2 combination DMARD therapies (MTX+SSZ+HCQ versus MTX+LEF+HCQ) in patient with early RA who have failed MTX monotherapy

Objectives :

1. To assess safety and efficacy of MTX+LEF+HCQ based combination DMARD therapy in patients with early RA failing MTX monotherapy
2. To assess safety and efficacy of MTX+SSZ+HCQ based combination DMARD therapy in patients with early RA failing MTX monotherapy
3. To compare the safety and efficacy profile of 2 combination DMARD therapy (MTX+LEF+HCQ and MTX+SSZ+HCQ)

Methodology

- A. Study design/type:** Randomized parallel group non-inferiority trial, pragmatic design
- B. Study participants:** Humans

For Participants

- a. Inclusion criteria :

Age >18 years satisfying ACR-EULAR criteria for RA

1. Polyarthritis (>4 joints)
2. Disease duration of less than 2 years
3. Patients with moderate to severe disease activity (DAS28 \geq 3.2)
4. Patients who have failed to respond to initial Methotrexate monotherapy

b. Exclusion criteria :

1. End stage disease (deformed fixed joints)
2. Patients with vasculitis, extra-articular features like interstitial lung disease
3. Contraindications to DMARD therapy (Chronic Alcoholism, Chronic liver disease, Evidence of acute/chronic infection, Chronic kidney disease, Patients with leucopenia ($<3.0 \times 10^9/l$), thrombocytopenia ($<150 \times 10^9/l$), AST/ALT $>2 \times$ upper normal value and creatinine clearance <30 ml/minute)
4. Pregnant, lactating women ; patients (both men and women) of reproductive age group unwilling for contraceptive use who have not completed the family
5. Patients unable to come for regular follow up

c. **Number of groups to be studied, their names and definitions:**

Group 1: MTX+LEF+HCQ

Group 2: MTX+SSZ+HCQ

C. Sampling

a. Sampling Population : Patients >18 years of age diagnosed with RA, attending OPD services of the Department of Clinical Immunology

b. Sample size calculation : (calculated for non inferiority trial)

Sample size has been estimated as 70 patients in each group using the N master software considering success rate as 75 % in both groups (calculated from FIN-RACo trial group, Lancet 1999 (13)) and non inferiority limit as 20% with 5 % alpha error ,statistical power of 80 % and dropout rate as 20%

c. Sampling technique: block randomization

D. Randomization details: block of 10, 1:1 random allocation.

E. Study Procedure

A. Selection of participants: All consecutive patients of RA attending the OPD services of the department of Clinical Immunology will be included to reach a minimum sample size of in each group.

[figure not shown]
B. Patients will be assessed for eligibility and will be started on Methotrexate monotherapy initially and then only patients, who have moderate to severe disease activity inspite of 12 weeks of Methotrexate monotherapy, will be randomized to either of the 2 groups of DMARDs.

C. Allocation to groups:

Allocation concealment will be done by : Sequentially numbered, opaque, sealed envelopes (SNOSE) method

Group 1: MTX+LEF+HCQ

Group 2: MTX+SSZ+HCQ

F. Data Collection method including settings and periodicity: Patients aged above 18 years diagnosed as RA according to the 2010ACR-EULAR criteria will be screened and evaluated for inclusion in the study. The patients will be examined every 2 week interval during DMARD dose escalation & then every month for next 6 weeks of MTX and for 24 weeks for either groups.

a. Clinical evaluation:

- i. Adverse drug reactions (ADRs) – each visit
- ii. IHAQ, DAS28 - once at baseline and then at 12 weeks of MTX monotherapy and then at the end of 24 weeks treatment with either of Group 1 or group 2 drug.

b. Laboratory:

- i. Routine CBC/RFT/LFT: every 2 week interval during dose escalation & then every month for 12 weeks after starting the drug
- ii. ESR & hsCRP for disease activity evaluation: every month.
- iii. **USG** wrist, hand and feet (US-7 score)- at baseline and at 12 weeks of Group 1 or group 2 drug

G. List of variables and their measurement methods with standardization techniques:

a. (i) Independent variables

Socio-demographic profile:

- Age
- Gender

b. Outcome Variables:

Disease-related parameters –

Primary outcome measures:

- a. Disease activity (state) - DAS28

Secondary outcome measures:

- a. Functional ability – iHAQ
- b. Mean changes over time in:
 - i. Inflammatory parameters: ESR, hs-CRP
 - ii. Disease activity as per US-7 score
- c. Adverse drug reactions

Primary endpoint:

Proportion of patients in both groups achieving good response according to European League Against Rheumatism (EULAR) response criteria at the end of 12 weeks of combination therapy

Secondary endpoint:

1. Change in functional ability (Indian Health Assessment Questionnaire; iHAQ) at the end of 12 weeks of combination therapy
2. disease activity by US7 score at 12 weeks
3. Safety of study medications (adverse drug reactions) during study period (till 24 weeks)
4. Proportion of patients achieving good EULAR response at the end of 24 weeks of combination therapy

Assessment of treatment response

The disease activity will be reassessed at the end of 12 and 24 weeks of random group allocation. The treatment response will be graded according to EULAR response criteria

Radiological assessment of disease activity

Musculoskeletal Ultrasound (**US-7 score**) will be performed in all patients in non blinded manner by the researcher

Clinical Evaluation :

- a. Demography: Age/Sex, ethnicity
- b. Detailed history and examination will be done for all patients
- c. Baseline evaluation of patient

Disease Activity: Indian Health associated questionnaire (IHAQ), Disease Activity Score-28 (DAS28)

Damage: Joint: Loss of motion, Deformity, Mal-alignment

- d. Extra-articular: Sicca symptoms & signs, sub cutaneous nodules, evidence of Interstitial Lung Disease (ILD), peripheral neuropathy, scleritis/episcleritis

Laboratory investigations

- i. **Routine:** Complete blood count (CBC), Erythrocyte Sedimentation Rate (ESR), Sugar (FBS/PP2BS), Liver Function Test (LFT), Renal function test (RFT), Mantoux Test, Viral markers (HIV, HBsAg, Anti HCV), urine analysis, Thyroid function test (TFT)

ii. **Ultrasound (USG)** wrist, hand and feet (US-7 score)

Immunological: High sensitivity C-reactive protein (hsCRP), Rheumatoid Factor (RF), Anti-CCP antibody (ACPA) in all participants .

After baseline evaluation, all consecutive patients with RA will be started on MTX monotherapy unless contraindicated. Patients not responding adequately to MTX monotherapy (DAS28 \geq 3.2) at the end of 12 weeks will be randomized to either of the 2 groups by block randomization after written informed consent.

- MTX+LEF+HCQ- Group 1
- MTX+SSZ+HCQ- Group 2

Concurrent treatment with the following drugs will be allowed during the study as per severity of symptoms and in cases of breakthrough pain:

1. Non-steroidal anti-inflammatory drugs (NSAIDs) - Tablet Diclofenac sodium 50mg twice a day (will be given for minimum duration) and if given on “as and when required” basis, patient will be asked to maintain an NSAID diary so as to know their requirement.
2. Oral low dose Glucocorticoids (GC) - 7.5 mg/d for 4 weeks followed by 5 mg/day for 2 weeks followed by 5mg on alternate day for 2 weeks – as a bridge therapy. Thereafter, it can be given if disease flares (patient being symptomatic with continued DMARD therapy), with the maximum dose being 7.5mg/day.
3. Intra articular steroids-will be allowed during the study, as per severity of patient’s symptoms. The number of intraarticular injections required in each group will be calculated.

DMARD dosages used are:

For all patients as a standard protocol for management of all patients with RA :

1. **MTX** – starting dose 10 mg/week orally for 2 weeks → 15mg / week for 2 weeks 20 mg/ week for 2 weeks → 25mg/ week → assessment of response to MTX after 6 weeks (at the end of 12 weeks after starting MTX)
2. In patients , not tolerating adequate doses of oral MTX in the form of nausea, vomiting, the following strategies will be adopted- 1) dose will be split into two 2) oral MTX will be converted to im formulation.
3. T. Ondansetron 4mg twice a day for 2 days a week will be allowed in the study if patient has nausea or vomiting with MTX.
4. T. Folic acid 5 mg twice a week

Those not achieving adequate response to a maximum permissible dose of MTX (25 mg / week) ie. DAS28ESR >3.2 will be enrolled in the study after randomization:

For **Group 1**

1. T. MTX will be continued at 25mg/week
2. T. folic acid 5 mg twice per week
3. T. LEF -10 mg/day starting dose for 2 weeks → 20mg /day
4. T. HCQ 200 mg/day at night

For **Group 2**

1. T.MTX will be continued at 25mg/week
2. T. Folic acid 5 mg twice a week
3. T.SSZ 500mg once a day for 7 days → 500mg twice a day for 7 days →
500mg thrice a day for 7 days → 1gram twice a day
4. T. HCQ 200mg/day at night

Note: During the course of the study any patients developing extra-articular manifestations requiring different mode of therapy will be excluded from study (but intention to treat analysis will be used for analysis of results).

STATISTICAL ANALYSIS PLAN (SAP)

The trial is designed as a non-inferiority pragmatic trial. The assessment will be done in unblinded fashion by the researcher. Arbitrarily considering EULAR good response rate (primary endpoint) of 75% with SSZ based triple regimen (tREACH and TICORA study) and non-inferiority margin of $\Delta = (-20\%)$ for LEF, a sample size of 140 (70 in each group) was determined using nMaster sample size calculator (version 2 software) using 2-sided confidence levels (CI) of 95%, power of 80% and dropout rate of 20%.

Data will be analyzed using SPSS (IBM pasw statistics, version 19.0) for windows. For quantitative data [DAS28ESR, iHAQ], normality of distribution will be checked by Shapiro-Wilks W test. Continuous data was presented as median and interquartile range (IQR₂₅₋₇₅) / mean with SD as appropriate. Mann-Whitney U test / Students t test will be used for comparison between median/ mean of 2 groups respectively. Qualitative or categorical variables (such as EULAR good response) will be described as proportions and will be tested using Chi-square. Odds ratio (OR) – odds of achieving the outcome (treatment response) in patients exposed to LEF in comparison to patients not exposed to LEF (SSZ group) along with 95% confidence interval and p-value will be used to study the statistically significant difference in treatment outcome between 2 groups. P-value of <0.05 was considered as significant.

The primary endpoint will be analyzed by both intention-to-treat (ITT) and per-protocol (PP) analysis. The rest of the parameters will be analyzed by ITT analysis only. Patients who do not complete the study, the last observation will be taken as their outcome for ITT analysis. For missing data, the last available readings will be carried forward in case of patients who are not available for the endpoint assessment. Non-inferiority testing will be done by using a 95% confidence interval (CI) of the difference between the proportions of patients achieving the primary endpoint between 2 groups. Extension of CONSORT 2010 statement will be used for reporting of non-inferiority of the LEF group.

DATA COLLECTION PROFORMA

CODE NO:

Date of enrollment:

Name/ age/ sex/ CCR no :

Contact number

Disease duration:

Co-morbid conditions (with duration):

Personal history (habits/addictions):

Treatment history:

Family history:

Baseline Investigations:

RF:

HIV:

HBsAg:

HCV:

Anti-CCP:

Mantoux test:

Drug

Dose

since when

Side effects

1

2

3

| | Baseline | 4mo | 5mo | 6mo |
|---------------|-----------------|------------|------------|------------|
| IA Steroids | | | | |
| Oral steroids | | | | |

| | Baseline | 4 week | 8 week | 12 week | 16 week | 20 week | 24 week |
|--------------------------|-----------------|---------------|---------------|----------------|----------------|----------------|----------------|
| TJ28 | | | | | | | |
| SJ28 | | | | | | | |
| VAS | | | | | | | |
| ESR | | | | | | | |
| hsCRP | | | | | | | |
| DAS28 | | | | | | | |
| iHAQ | | | | | | | |
| Morning stiffness | | | | | | | |

| | | | | | | | |
|--------------------------------|--|--|--|--|--|--|--|
| Extraarticular features | | | | | | | |
| Adverse drug reactions | | | | | | | |

FOLLOW UP INVESTIGATIONS

| Investigations | Baseline | 4W | 8W | 12W | 16W | 20W | 24W |
|-----------------------|-----------------|-----------|-----------|------------|------------|------------|------------|
| Hb | | | | | | | |
| TLC | | | | | | | |
| DLC | | | | | | | |
| MCV | | | | | | | |
| Platelets | | | | | | | |
| Peripheral smear | | | | | | | |
| Urine albumin | | | | | | | |
| Microscopy | | | | | | | |
| Blood urea | | | | | | | |
| Sr. Creatinine | | | | | | | |
| Bilirubin (T/D) | | | | | | | |
| AST/ ALT | | | | | | | |
| ALP/GGT | | | | | | | |
| Total protein /Alb | | | | | | | |
| CPK / LDH | | | | | | | |
| Sugar (AC/PC) | | | | | | | |
| CH/TG/HDL/LDL | | | | | | | |
| CT/USG/MRI | | | | | | | |
| ECG/ECHO | | | | | | | |

| US7 Score | | Baseline | 12 week | 24 week |
|------------------|-----------|-----------------|----------------|----------------|
| Synovitis | GS | | | |
| | PD | | | |
| TS | GS | | | |
| | PD | | | |
| Erosion | GS | | | |

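### A single fixed block of 10 in a one-clinic trial with unblinded assessment lets a recruiter who knows the block size and keeps count foresee about 1 in 6 allocations; a list with the same imbalance limit is less predictable

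*Combined protocol and SAP*

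**What the plan says.** Under Methodology, the sampling item gives "Sampling technique: block randomization" and item D (Randomization details) gives "block of 10, 1:1 random allocation". No other block size and no stratification factor is stated. The sampling population is patients "attending OPD services of the Department of Clinical Immunology", so there is one clinic and one list. The SAP's first paragraph states that "a sample size of 140 (70 in each group) was determined", which is exactly 14 blocks of 10.

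Study Procedure, item C, conceals allocation by "Sequentially numbered, opaque, sealed envelopes (SNOSE) method". On assessment, the SAP says "The assessment will be done in unblinded fashion by the researcher", and the ultrasound is done "in non blinded manner by the researcher". No masking of treatment is described, and the two regimens have visibly different dose schedules.

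The documents do not say who generates the list, who fills or opens the envelopes, or whether recruiting staff are kept from the block size.

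**The concern.** With one clinic, one list, visible treatments and one block size written in the protocol, anyone who enrols patients can keep a running count. Once five patients in a block have gone to one arm, every remaining allocation in that block is fixed. Because the envelopes are numbered in sequence, the number also shows the position in the block: envelopes 10, 20, 30 and so on are always determined by the nine before them.

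At stake is selection at entry. If the next arm is known or can be guessed, the decision to enrol a particular patient, or the timing of enrolment, can differ by arm. In a non-inferiority comparison this can move the difference in either direction. Neither the ITT nor the per-protocol analysis corrects for who was let in. The SAP plans an unadjusted chi-square test, odds ratio and confidence interval for the difference, so measured baseline differences would not be adjusted for, and unmeasured ones could not be.

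**Working it through.** **Inputs.** Block 10 (5 + 5), 1:1 (Methodology, item D). N = 140 (SAP). Response 75% in both arms, margin 20 points, 5% alpha, power 80%, dropout 20% (sample size item).

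**The plan's own figure.** N matters here only because it sets the number of blocks. With "considering success rate as 75 % in both groups" and one-sided 5%: n = 2 × 0.75 × 0.25 × (1.645 + 0.842)² / 0.20² = 57.96, so 58; 58 × 1.2 = 69.6, so 70 per arm. This matches. (The SAP's two-sided 95% level would give 74 before dropout; that is a separate matter.) 140 / 10 = 14 blocks.

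**Forced allocations, fixed block of 10.** Position k + 1 is forced if one arm already has five patients among the first k. The probability is 2 × C(k,5) / C(10,5), with C(10,5) = 252:

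| Position | Calculation | Probability forced |
|---|---|---|
| 6 | 2 × 1 / 252 | 0.8% |
| 7 | 2 × 6 / 252 | 4.8% |
| 8 | 2 × 21 / 252 | 16.7% |
| 9 | 2 × 56 / 252 | 44.4% |
| 10 | 2 × 126 / 252 | 100% |

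The sum is 1.667 per block, a share of 1/6 (16.7%). Over 14 blocks: 14 × 1.667 = 23.3 of 140.

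**Best-guess success, fixed block of 10.** Always guess the arm that is behind. For a block of 2m, expected correct guesses are m + (2^(2m) / C(2m,m) − 1) / 2. With m = 5: 5 + (1024/252 − 1) / 2 = 6.53 of 10, or 65.3%.

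**Big stick, maximum imbalance 5.** A fair coin is used unless the difference is 5; then the next allocation is forced. A block of 10 also reaches at most 5. An exact chain over 140 allocations gives 9.4% forced (13.2 of 140). The coin is fair at every other step, so the guess rate is 0.5 + 0.5 × 0.094 = 54.7%. The final difference is −4, −2, 0, 2 or 4 with probability 0.2 each: mean absolute difference 0.2 × (4 + 2 + 0 + 2 + 4) = 2.4, maximum 4.

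**Maximal procedure, limit 5, ending 70:70.** All sequences that respect the limit are equally likely. The exact path count gives 3.3% certain (4.6 of 140) and 58.9% guessed.

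**Randomly ordered blocks.** Simulated, for an observer who knows the set of sizes but not their order and updates on each allocation.

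| Scheme | Certain | Guessed | Excess over 50% | Worst imbalance |
|---|---|---|---|---|
| Fixed block of 10 | 16.7% | 65.3% | 15.3 | 5 |
| Big stick, limit 5 | 9.4% | 54.7% | 4.7 | 5 |
| Maximal procedure, limit 5 | 3.3% | 58.9% | 8.9 | 5 |
| Blocks 8/10/12/14 | 0.6% to 0.7% | about 64.5% | about 14.5 | 7 |
| Blocks 4/6/8 | about 2.4% | about 68% | about 18 | 4 |

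The big-stick and maximal-procedure figures already assume that the observer knows the limit.

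**Power cost of unequal arms.** With 140 analysed, SE = √(0.1875 × (1/n₁ + 1/n₂)) and power = Φ(0.20/SE − z). One-sided 5%: 86.16% at 70:70 and 86.14% at 72:68. One-sided 2.5%: 78.01% and 77.98%.

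**Scale of possible bias (assumption, not a document figure).** Suppose only forced allocations are steered, so that those patients' response probability is d higher in one arm and d lower in the other. The difference then shifts by d/6 + d/6 = d/3. For d from 5 to 20 points that is 1.7 to 6.7 points, against a margin of 20.

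**The case against.** The plan contains no error or contradiction here. Permuted blocks with opaque sealed envelopes are a valid scheme, and 10 is a fairly large block. The usual substitute, small varied blocks, would raise the guess rate (4/6/8: about 68%). That stands, and it is why small varied blocks are not recommended.

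The room for selection is also narrower than it first looks. Study Procedure, item A, calls for consecutive enrolment. Candidates are identified about 12 weeks earlier, when methotrexate starts, and entry follows a numeric DAS28 rule that includes ESR, a laboratory value. This stands in part. Joint counts, the patient's VAS, the exclusion for inability to attend follow-up, and consent taken at randomization still leave discretion, and no screening-log check is described.

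Unblinded outcome assessment is arguably the larger threat, since it can touch every patient, and a new list does nothing about it. That is true, but it is no reason to leave entry predictable as well.

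A reader might infer three stronger things that the documents do not support:

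- **That 1 in 6 allocations are simply known in advance.** The figure holds only for someone who knows the block size and has tracked the earlier allocations. The documents do not show that any recruiter did so, or that recruiter and list-holder are the same person.
- **That the block size was public during recruitment.** The documents show only a protocol dated 2016 and a covering letter to the registry dated 2021.
- **That any alternative is free and equally good.** Big stick gives up exact balance, and blocks of 8/10/12/14 lower the guess rate by under one point.

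**Conclusion.** The point holds as an inexpensive improvement to the design, not as an error. A fixed block of 10 leaves 16.7% of allocations (23.3 of 140) foreseeable with certainty, and 65.3% guessable, to a recruiter who knows the block size and keeps count. Nothing in the documents withholds the block size or otherwise removes this.

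At the same N and the same worst-case imbalance, big stick cuts the guessing excess from 15.3 to 4.7 points, and the maximal procedure cuts certain allocations about fivefold. The conclusion rests on one unstratified list and on treatment being open, which is inferred from the unblinded assessment and the absence of any described masking. No bias is shown to have occurred, and its possible size depends on an assumption that the documents cannot settle.

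**What to change.** Before the envelopes are filled, replace the block of 10 in Methodology, item D, with one of these:

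- **Preferred:** a big-stick list with maximum imbalance 5.
- **If exactly 70:70 is wanted:** the maximal procedure with the same limit. It leaves fewer certain allocations than big stick but a higher guess rate.
- **Weaker alternative:** randomly ordered blocks of 8, 10, 12 and 14. Certain allocations nearly vanish, but guessing barely changes and the worst-case imbalance rises to 7.

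Keep the limit or block sizes out of the protocol that recruiters hold. State that the list and envelopes are prepared by someone who neither enrols nor assesses patients.

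The cost is a new computer-generated list and one changed sentence; the same envelopes serve. For big stick, final arm sizes differ by 2.4 patients on average and at most 4, and power falls by less than 0.1 point. The maximal procedure leaves N and final balance unchanged.

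### Compare the continuous outcomes by ANCOVA on the randomisation-visit value, and name that visit as the reference for EULAR response and the change scores

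*Combined protocol and SAP*

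**What the plan says.** Study Procedure, section F, Clinical evaluation item ii, schedules DAS28 and iHAQ twice before any combination therapy: "IHAQ, DAS28 - once at baseline and then at 12 weeks of MTX monotherapy". Patients are randomised at the end of those 12 weeks, so the second value is a measurement at randomisation. ESR and hs-CRP are taken monthly (section F, Laboratory).

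The SAP (second paragraph) names DAS28-ESR and iHAQ as quantitative data. It checks normality by Shapiro-Wilk and then compares the groups by Student's t test or Mann-Whitney U test. It mentions no covariate and does not say whether the tests apply to the final value or to change.

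The primary endpoint is "Proportion of patients in both groups achieving good response according to European League Against Rheumatism (EULAR) response criteria" after 12 weeks of combination therapy. The first secondary endpoint is "Change in functional ability (Indian Health Assessment Questionnaire; iHAQ) at the end of 12 weeks of combination therapy". Both give the time of the outcome; neither gives the visit it is compared with.

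**The concern.** There are two linked issues.

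**Precision.** A two-group test that ignores the randomisation value, or only subtracts it, has a larger variance than a model that includes it as a covariate. The data are already collected, so the plan gives up precision on iHAQ, DAS28, ESR and hs-CRP for nothing.

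**Reference visit.** Adjustment and change scores both need one named starting value, and the plan has two candidates. If EULAR good response depends partly on a fall in DAS28, the choice also affects the primary endpoint. A pre-MTX reference would credit improvement on MTX alone to each combination, and would change the quantity to which the 20-point margin applies.

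**Working it through.** **1. Figure to reproduce.** None. The plan gives no precision or power figure for a continuous outcome. The 70 per group rests on the binary primary endpoint and is not affected by this point.

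**2. Inputs.** Let ρ be the correlation between the randomisation value and the follow-up value within an arm. The documents give none, so 0.3, 0.5 and 0.6 are assumed. Equal variance σ² at the two visits is also assumed.

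**3. Formulas (variance per patient).**
- Final value: σ²
- Change from randomisation: 2σ²(1 − ρ)
- ANCOVA: σ²(1 − ρ²)

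ANCOVA relative to final value is 1 − ρ². Relative to change it is (1 − ρ)(1 + ρ) / [2(1 − ρ)] = (1 + ρ)/2. Relative confidence-interval width is the square root of each.

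| ρ | Variance v final value | Variance v change | CI width v final value | CI width v change |
|---|---|---|---|---|
| 0.3 | 0.91 | 0.65 | 0.95 | 0.81 |
| 0.5 | 0.75 | 0.75 | 0.87 | 0.87 |
| 0.6 | 0.64 | 0.80 | 0.80 | 0.89 |

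**4. Skewed iHAQ.** Simulation under assumed values: 0-3 score in steps of 1/12, beta margins joined by a Gaussian copula, latent shift of 0.45 SD, 70 per arm, 6,000 trials per cell.

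| Skewness, ρ | t test | Mann-Whitney | ANCOVA | Rank ANCOVA |
|---|---|---|---|---|
| 0.8, 0.5 | 71% | 73% | 81% | 84% |
| 1.4, 0.5 | 65% | 71% | 74% | 81% |
| 1.4, 0.3 | 64% | 71% | 67% | 74% |

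Entries are power. Type I error was 4.4-5.6% for every test. In the last row ordinary ANCOVA falls below Mann-Whitney while rank ANCOVA does not.

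**5. Which visit is the reference?** The passages side by side:
- *For pre-MTX:* section E.B, "Patients will be assessed for eligibility and will be started on Methotrexate monotherapy initially", and the paragraph on starting treatment, "After baseline evaluation, all consecutive patients with RA will be started on MTX monotherapy unless contraindicated". Both put the baseline work-up before MTX.
- *For randomisation:* failure of MTX is an inclusion criterion; written consent is placed at randomisation; the response paragraph says "The disease activity will be reassessed at the end of 12 and 24 weeks of random group allocation"; the DMARD dosages section places enrolment after randomisation; and the proforma opens with an enrolment date. The proforma's disease-activity table (Baseline, then weeks 4 to 24) reaches week 24 of combination therapy only if its Baseline is randomisation.
- *Fits neither fully:* the proforma's steroid table (Baseline, 4, 5 and 6 months). Counted from randomisation it skips months 1-3 of combination therapy; counted from the start of MTX it misses weeks 13-24 of combination therapy.

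**6. Size of the effect on the response rate.** The documents do not give the EULAR criteria. Assume good response means DAS28 ≤3.2 with a fall of more than 1.2. Assume also normal DAS28 with SD 1.0, pre-MTX mean 5.0-6.0, mean fall on MTX 0.5-1.2, mean 2.4-3.2 after 12 weeks of combination, correlation 0.3 or 0.6 between successive visits, and DAS28 ≥3.2 at both earlier visits.
- Over twelve such settings the pre-MTX reference raises the rate by 1.2 to 4.9 points and classifies 1.9% to 9.1% of patients differently.
- Near the planned 75% (means 5.5, 4.8 and 2.4), the rate goes from 73.6% to 76.3% at correlation 0.3, and from 74.6% to 76.4% at 0.6.
- A wider grid of assumed means, SDs and correlations, limited to settings with a randomisation-anchored rate of 70-80%, gives rises of 0.2 to 7.6 points (median 2.8).

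**The case against.** **The planned tests are valid, so ANCOVA is a preference.** The first half stands: randomisation protects the t and Mann-Whitney comparisons, and a test on change from randomisation already uses that value. What remains is a precision gain at almost no cost. The objection that skewed iHAQ can favour Mann-Whitney over ordinary ANCOVA also stands in part (step 4, last row). It is met by specifying a rank-based version in advance.

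**The reference visit is obviously randomisation.** Most of the text supports this, and one figure next to section E.B is not reproduced and might show it. So this is a clarification; the primary endpoint is not left wholly undefined. But only the outcome time and the enrolment point are fixed in readable text, and the procedures use the word baseline for the pre-MTX visit.

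**Stronger readings that a reader might infer.**
- *That a pre-MTX reference biases the comparison.* It does not. With equal arms and the same reference in both, the expected difference is zero.
- *That it loses control of the false-positive rate.* The documents do not support this. In one assumed example (DAS28 means 5.5, 4.5 and 2.25, SD 1, correlation 0.5, 70 per arm), a 20-point deficit counted from randomisation is about 17.7 points counted from pre-MTX, and non-inferiority is declared in 5.1% of trials instead of 2.5%. Set the deficit at 20 points on the pre-MTX count, and the figures are 2.4% (pre-MTX) and 1.1% (randomisation). Each reference, once fixed, holds about 2.5% against its own null. The difference is a change in what is estimated, and no document says which null is the true one.

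**Dropout dilutes the shift.** Under last observation carried forward, a patient lost before any later DAS28 carries a value of at least 3.2 and is essentially a non-responder on either count. With 20% such patients, 1.2-4.9 points becomes 0.8 × 1.2 = 1.0 to 0.8 × 4.9 = 3.9.

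**Conclusion.** The point holds as an inexpensive improvement with a supporting clarification.

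- **Analysis.** ANCOVA on the randomisation value would cut the variance by 9-36% against a final-value comparison and by 20-35% against change from randomisation, for assumed correlations of 0.3-0.6 and equal variances. It concerns secondary outcomes only and corrects no bias.
- **Reference visit.** The readable text does not name it, though most of it favours randomisation. If good response includes a fall in DAS28, which is an assumption, a pre-MTX reference would raise each arm's rate by a few points and alter what the 20-point margin is applied to. The assessor is unblinded, so the reference should not remain open once data can be seen.
- **US-7.** The schedule reads "wrist, hand and feet (US-7 score)- at baseline and at 12 weeks of Group 1 or group 2 drug"; on the procedures' use of the word baseline, no scan falls at randomisation. The second secondary endpoint is already a 12-week status comparison, so only the separate listing of US-7 under mean changes needs care.

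**What to change.** 1. **SAP, continuous outcomes.** Analyse iHAQ and DAS28 at 12 and 24 weeks of combination therapy, and log-transformed ESR and hs-CRP, by ANCOVA with treatment group and the randomisation-visit value. Remove the Shapiro-Wilk step as the way of choosing the test. Prespecify rank-based ANCOVA for iHAQ as a sensitivity analysis that is always run.
2. **SAP, primary analysis.** Keep the unadjusted risk difference with its 95% confidence interval for non-inferiority.
3. **Reference visit.** Reconcile sections E and F, the treatment-start and response paragraphs and the proforma by naming the randomisation visit (end of 12 weeks of MTX) as the reference for EULAR response and for change in iHAQ, ESR and hs-CRP. Label the proforma's Baseline column accordingly, with a separate column if pre-MTX values are kept.
4. **US-7.** Report the 12-week score as a comparison between groups, and do not describe change from a pre-MTX scan as change on combination therapy.

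Cost: a few sentences in the SAP, a proforma label and a standard regression. Sample size is unchanged. DAS28 and iHAQ are already measured at randomisation, and ESR and hs-CRP monthly.
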